#### C.6. Description of the RCT.

For the RCT, 100 AYLHIV with a positive self-report or urine ADU test (based on data from the cross-sectional survey) will be randomly recruited from the six clinics and randomly assigned at the clinic level (3 clinics per group) to either the control (n = 50) or intervention (n = 50) group. The intervention will be delivered over a period of six months, and with assessments at baseline, and 6 months (end intervention). Upon completion of the RCT, AYLHIV will be randomly selected to participate in two FGDs (n=10 from control group and n=10 from intervention group). AYLHIV in the intervention group will share how the intervention affected their alcohol/drug use as well as their recommendations on how to tailor/improve the intervention to be more culturally appropriate and effective in reducing ADU among AYLHIV in Uganda, while AYLHIV in the control group will share their experiences with ADU risk reduction sessions and how this influenced their ADU.

**Description of the control condition:** AYLHIV in the control condition will receive ADU risk reduction sessions tailored for AYLHIV. Working with [name] (Consultant), we plan to adapt, expand and tailor the Program for Appropriate Technology in Health (PATH) Life Planning Skills curriculum (Unit 11 on substance use), to

include issues specific to AYLHIV. We will train research assistants, using an adapted facilitator's manual, to deliver the adapted curriculum. As part of the RCT, AYLHIV will complete a questionnaire (at baseline and end of the intervention) on their alcohol/drug use behaviors (self-report and biologically measured) and risk/resilience behaviors.

**Description of the intervention group:** In addition to the adapted ADU training module that the control group will receive, AYLHIV in the intervention arm will receive four (4) Financial Literacy (FL) training sessions and a Youth Development Savings account (YDA) for long-term savings. Although akin to conditional cash transfer interventions, which have become increasingly popular in the social development field by enabling individuals to meet basic needs while incentivizing pro-social behaviors, EE interventions that apply matched savings accounts go beyond incentivizing behavior. They emphasize long-term investment and promote life-long financial inclusion by forming savings habits and establishing partnerships between the participants and local financial institutions and the actual intervention program. For the proposed study, the FEE intervention will be in the form of a YDA, where savings are housed at a local bank and deposits made by the adolescent are matched by the intervention to encourage savings. YDAs yield positive effects, including creating a greater sense of security, self-confidence, and future orientation for young people. Each AYLHIV in the FEE intervention will receive a YDA held in their own name in a bank registered by the Central Bank (Bank of Uganda). We will form partnerships with national banks operating in the study area. The account will then be matched with money from the program. The maximum Adolescent's contribution to be matched by the program will be an equivalent of US \$20 per month per Adolescent or US \$120 for the 6-month intervention period. Our prior studies indicate that the partner financial institutions have multiple and easily accessible deposit locations in the study area, and that participants can save these amounts. Youth who save the maximum amount will have a total of \$240 at the end of the intervention (\$120 in savings plus \$120 from the match: a 1:1 match). As in the studies that inform this application, each month, a bank account statement will be generated for every AYLHIV to note their accumulated savings. The statements are intended to act as "morale boosters" for the enrolled AYLHIV/ Unique to this study is our innovative spending model, which empowers participants to make informed financial decisions. During the intervention period, AYLHIV will have direct access to both their personal savings deposited in the accounts as well as the match provided by the study. This is different from our prior studies that required the participants' own savings and the match to be kept in separate accounts and to get approval by the research team to access the match. This added unconditional component provides AYLHIV with a safety net to address short-term medical needs and financial and consumption emergencies if they arise. Participants will be provided with financial literacy sessions and mentorship tailored specifically to the needs of AYLHIV and ADU. We expect AYLHIV to be equipped with the knowledge to make well-informed consumption and expenditure decisions, but also feel supported in case of immediate medical needs. The research team will monitor, but not restrict, how participants spend their match. Additionally, the study team will have access to and review participants' bank statements to ascertain deposit and withdrawal frequency. Participants will be encouraged to utilize financial diaries to record their expenditures.

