**A.2. THEORETICAL FRAMEWORK.** Our conceptual approach is informed by the socio-ecological model (SEM), social causation and drift theories, and asset theory. We have applied the SEM as a basis for investigating the contextually relevant risk and resilience factors for ADU. SEM posits that environmental factors fall into four broad domains: micro-, meso-, exo-, and macro systems and interactions within and between these domains determine behavior. This model has demonstrated effectiveness in identifying risk and resilience factors for prevention planning and intervention for ADU. Social causation and social drift theories suggests that problem alcohol drinking may be both a response to and driver of poverty. Acute and chronic stress associated with living in a poverty-impacted environment increases the likelihood of ADU, which causes further material/economic deprivation, hence fueling the cycle of alcohol misuse, and contributing to downward social mobility. Research in Uganda has reported a higher burden of alcohol and drug abuse among poor populations, and many poverty-impacted Ugandan households engage in informal alcohol production for income-generating purposes. Impoverished youths are burdened with hopelessness due to lack of opportunities for improvement in their economic wellbeing. As a result, for impoverished AYLHIV, they may be inclined to spend on instant pleasures such as alcohol and drugs as a coping mechanism since they are less likely to believe they can afford the costs associated with accessing and maintaining long-term care for HIV. Our proposed FEE intervention is based on Asset theory and is intended to improve economic wellbeing and relieve poverty and its related consequences such as poor mental health, and create a more hopeful/optimistic outlook for the future, thus reducing AYLHIV's engagement in risk-taking behaviors including alcohol and drug use. The proposed FEE will be one of the first studies to primarily examine the impact of FEE interventions on reducing ADU among AYLHIV in poverty-impacted communities.

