## C.3. Inclusion criteria.

The target populations for this study are: 1) AYLHIV, 2) healthcare providers at the selected HIV clinics. All study participants will be recruited from the selected HIV clinics. **Inclusion criteria for clinics:** 1) located in the - fishing districts with known HIV hotspots (i.e. 2 randomly selected clinics per district); 2) accredited by the Uganda Ministry of Health as a provider of ART; 3) currently have established services for AYLHIV. **Inclusion criteria for AYLHIV:** 1) male or female AYLHIV aged 18-24 years 2) medically diagnosed with HIV and aware of their HIV status; 3) enrolled in care at one of the selected HIV clinics. **Inclusion criteria for health providers:** health providers (1 - 2 per clinic) will be recruited from each of the selected clinics. **Inclusion criteria for participants of the RCT:** a sub-sample of AYLHIV (n=100) with a positive self-report for ADU will be randomly selected and randomly assigned at the clinic level (3 clinics per group) to either an intervention group (n=50) or a control group (n=50). AYLHIV from the control (n=10) and intervention groups (n=10) will participate in two FGDs at the end of the intervention.

**Exclusion criteria for RCT and post-intervention FGD:** any AYLHIV with negative self-report for ADU. **Exclusion criteria for all participants:** anyone with a significant cognitive impairment that interferes with their understanding of the informed consent process, or who is unable/unwilling to consent.

Table 1.

SOCIO-ECOLOGICAL FRAMEWORK		Time collected
Level	Risk/protective factor	
Individual	Socio-demographic: Gender; Age; orphanhood; education, income and unemployment; food insecurity  ; experienced homelessness; refugee; day/boarding school; urban/rural residence. Mental health: Depression,  hopelessness,  Optimism  ; Stress,  pain,  history of substance abuse 	CS, QI, FGD, RCT
Interpersonal/ Relationship	Loneliness  ; number of close friends; bullying; interpersonal violence;  social support  ; family cohesion  ; childhood abuse/trauma;  family history of substance abuse,  sexual risk-taking 	
Community	Community norms; access to alcohol and illegal drugs	
Society	Educational campaigns; price and supply of alcohol, social stigma 	

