
#### C.7.1 Quantitative Data analysis.

**Analysis of cross-sectional survey data:** Frequency distributions and summary statistics for the outcome and all predictor variables will be derived. The prevalence of ADU from both biological tests and self-reports, assessed using the Smoking and Substance Involvement Screening Test (NIDA-Modified ASSIST) among AYLHIV, will be calculated by dividing the number who tested positive for ADU by the total number of participants tested, and dividing the number screened to be of moderate or high risk in self-reported data by the total number of participants who completed the survey. To determine which multilevel factors are associated with substance misuse, we will fit logistic regression models comprising the outcome (ADU) and potential risk factors with standard errors adjusted for clustering by clinics.

**Analysis of RCT data:** Primary hypothesis. We hypothesize that participants in the intervention group will have a lower odds of ADU compared to participants in the control group. To test this hypothesis, we will fit three-level mixed-effects models. Each model will comprise the outcome, and fixed categorical effects for study group (intervention vs control), time (baseline, 6-months), and a group-by-time interaction term. Random intercepts will be fitted at the clinic and person level, with unstructured correlations among subjects' repeated measures. Robust Huber-White standard errors and test statistics will be computed for each model. We will assess the omnibus effects for study group, time, and their interaction. Post-estimation analyses will be conducted to assess time-within group simple effects and group within time simple effects. Secondary hypothesis. We hypothesize that AYLHIV in the intervention group will have better mental health outcomes including lower levels of

depressive symptoms, less hopelessness, improved adherence and achieve better viral suppression and improved economic outcomes than AYLHIV in the control group.

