**Assessing the Feasibility of Economic Approaches to Prevent Substance Abuse Among
Adolescents**

NCT Number: NCT05597865

Statistical analysis plan updated June 20th 2025

The primary study outcomes were feasibility and acceptability of the research protocol, assessed using a mixed methods approach. Quantitatively, feasibility will be determined by the proportion of participants who enrolled in the intervention. Acceptability will be determined by measuring retention rates at 6 months, adherence to study procedures, intervention attendance and engagement. To assess whether participants adhered to and engaged in the intervention components we will report descriptive statistics to track the number and percentage of participants completing each intervention session, and the retention rate at the 6-month follow-up.

To examine short-term outcomes of the randomized controlled trial (RCT), with a focus on changes in prevalence of alcohol and drug use and psychosocial variables from baseline to 6-months. Categorical variables will be summarized using counts and percentages, and continuous outcomes will be summarized using means and standard deviation (SD) for the overall group and by study arm. Following noted experts and NIH guidance, we acknowledge that pilot RCT studies are too small to allow for sufficiently powered statistical tests or reliable effect size estimates to be determined or to conduct formal tests of clinical outcomes. In addition, attempting to obtain precise estimates of effect sizes cannot be statistically justified. Thus, in this pilot RCT we will focus on feasibility and acceptability of the protocol- design and adjustments necessary to maximize recruitment, retention, and quality assessment of outcomes in future studies.

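### The yes/no alcohol and drug use outcome cannot register heavier use among participants who already use, and neither document plans a by-arm summary of it

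*Protocol*

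**What the plan says.** **Who enters.** Protocol Section C.3 states that "a sub-sample of AYLHIV (n=100) with a positive self-report for ADU will be randomly selected and randomly assigned", and it excludes "any AYLHIV with negative self-report for ADU". Section C.6 describes the entrants differently, as "100 AYLHIV with a positive self-report or urine ADU test (based on data from the cross-sectional survey". Section C.2 adds that people who report use but test negative in urine may still enter the RCT.

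**Design.** Participants are "randomly assigned at the clinic level (3 clinics per group) to either the control (n = 50) or intervention (n = 50) group". Both arms receive the ADU risk reduction sessions. The intervention arm also receives financial literacy training and a savings account matched 1:1 on the participant's own deposits, up to US $20 per month for six months. Savings and match are both accessible during the intervention, and "The research team will monitor, but not restrict, how participants spend their match".

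**How ADU is analysed in the RCT.** Section C.7.1 hypothesises that "participants in the intervention group will have a lower odds of ADU compared to participants in the control group" and fits mixed models with group, time and their interaction. The SAP, dated later, describes the short-term outcomes "with a focus on changes in prevalence of alcohol and drug use" and psychosocial variables. It summarises them overall and by arm, and it disclaims formal tests of clinical outcomes. Neither document defines the RCT ADU outcome. The only self-report cut-off appears in Section C.7.1 for the survey, where moderate and high risk on the NIDA-Modified ASSIST (NM-ASSIST) are pooled as positive.

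**What else is collected.** Table 1 lists self-reported use, urine tests, depressive symptoms, hopelessness, adherence, viral load and sexual risk-taking for the RCT. Section C.6 adds review of bank statements, optional spending diaries and an end-of-trial focus group of 10 intervention participants.

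**The concern.** People chosen because they use alcohol or drugs are given money they may spend as they wish, and the outcome records only whether they use. Such an outcome can show people stopping. It cannot show people who go on using and use more. If it also repeats the entry criterion, almost nobody has room to become newly positive.

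This matters for the next step. The Specific Aims say that the findings may inform a larger R01 trial. Section C.6 presents the spending model as different from the team's earlier studies, where the match sat in a separate account and needed approval, so on the protocol's own account those studies did not test open access. Whether anyone escalated, and in which arm, is a question that the pilot's planned data could describe, but no analysis asks it.

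**Working it through.** **1. The plan's own figures.** $20 × 6 = $120 saved, plus $120 match = $240, as Section C.6 states. The documents give no sample-size derivation, alpha, power, ADU rate, effect size or intraclass correlation (ICC), so there is nothing further to reproduce. Inputs below that are not in the documents are marked as assumed.

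**2. Room for new positives.** With 50 per arm, the number who can turn positive is 50 × (1 − baseline prevalence):

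| Baseline prevalence (assumed) | 100% | 95% | 90% | 80% | 60% |
|---|---|---|---|---|---|
| Can turn positive, per arm | 0 | 2.5 | 5 | 10 | 20 |

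The 100% column applies only if the outcome repeats the entry measure and status has not changed by RCT baseline.

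**3. What a yes/no outcome registers.** With moderate and high risk pooled:

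| Baseline to 6 months | Recorded as |
|---|---|
| Below cut-off to moderate or high | Worse |
| Moderate to high | No change |
| High to moderate | No change |
| Moderate or high to below cut-off | Better |

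The second row is the gap. An any-use definition or a urine result behaves the same way, because a positive stays positive under heavier use.

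**4. Example (assumed counts).** Fifty people in an arm are all at moderate or high risk at baseline. Ten fall below the cut-off and ten go from moderate to high. Prevalence goes from 50/50 = 100% to 40/50 = 80%. The escalations are 10/50 = 20% of the arm and are not counted.

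**5. Simulation (all inputs assumed).** 2,000 runs per scenario; 50 per arm; no clustering or dropout; use-days among users lognormal with median 6 and log-SD 0.8, rounded and limited to 1–30; equal 6-month prevalence in both arms; users in the intervention arm have 1.25, 1.5 or 2 times the use-days; two-sided 0.05. Percentage of runs that flag a difference:

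| Prevalence | Yes/no (Fisher): 1.25 / 1.5 / 2 | Use-days (Mann-Whitney): 1.25 / 1.5 / 2 |
|---|---|---|
| 100% | 0 / 0 / 0 | 28.5 / 69.5 / 99.3 |
| 90% | 1.9 / 2.0 / 2.0 | 18.5 / 51.8 / 90.2 |
| 70% | 2.5 / 2.1 / 3.9 | 9.9 / 22.1 / 50.5 |

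Clinic clustering would lower the power of a valid use-days test. The contrast between the columns is the point, not the levels.

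**6. What the yes/no comparison can still show.** If control falls to 80% and intervention stands at 95%, the arms differ visibly. Mean clinic size is 100/6 = 16.7, so effective n per arm = 50 / (1 + 15.7 × ICC), which gives 50, 28.0 and 19.5 at assumed ICCs of 0, 0.05 and 0.10. Power at two-sided 0.05 is 62%, 39% and 29%. For 70% against 85% it is 43%, 27% and 20%. A 15-point excess at 80% power needs 76 per arm (control 80%) to 170 (control 50%) before clustering.

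**7. The ceiling case in the model.** At exactly 100% baseline, the odds are infinite and a logistic group-by-time interaction has no finite estimate. Only the 6-month contrast remains.

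**8. How much reassurance zero events would give.** If none of 50 escalates, the two-sided 95% upper limit is 1 − 0.025^(1/50) = 7.1%. This assumes 50 independent, fully followed participants. With effective n of 28.0 or 19.5, the same formula gives about 12% or 17%.

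**The case against.** Several stronger readings are tempting, and the documents do not support them.

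- **That ADU certainly starts at 100%.** The RCT outcome is undefined. Entry status comes from the survey (October to December 2022), RCT recruitment starts in February 2023, and ADU is measured again at RCT baseline. Urine-negative entrants are allowed. Baseline can therefore be below 100%, and a urine outcome can rise.
- **That nothing could reveal worsening.** The Section C.7.1 group, interaction and group-within-time effects are not restricted to benefit, and the SAP reports prevalence by arm against an active control. A fall in one arm alone would not count as benefit. Mental health, adherence and viral load are outcomes as well, and the focus group asks how the intervention affected use.
- **That the protocol predicts this harm.** Section A.2 says of impoverished young people with HIV that "they may be inclined to spend on instant pleasures such as alcohol and drugs as a coping mechanism". That sentence describes use driven by poverty, and the section goes on to argue that the intervention should reduce it. Heavier use through easier access to money is a reviewer's hypothesis.
- **That a move from low to high risk would go unseen.** It would cross the only stated cut-off and count as worsening.
- **That the arm receives a free grant.** The match depends on the participant's own deposits. It is unrestricted in use only.

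All five corrections stand. None reaches the second row of the table in step 3: prevalence by arm shows more people positive, not heavier use among those already positive. The SAP's means and SDs for continuous outcomes could cover a score, but it names none for ADU, and a mean can hide improvers and worseners who cancel out. The focus group reaches 10 of 50, and no analysis is stated for bank statements or diaries.

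**Conclusion.** The point holds as a gap in the planned analysis, not in data collection or in the choice of intervention. Under any yes/no definition, escalation among existing users counts as no change. That conclusion needs no assumption about baseline prevalence. The ceiling is an additional and conditional problem, present at or near 100% only if the outcome mirrors the entry criterion. The yes/no comparison can show relative harm, but with little power: 62% for 80% against 95% without clustering and 29% at an ICC of 0.10, before allowing for only three clinics per arm. The simulated contrast (0% against 99% when use doubles and everyone is positive) rests wholly on assumed inputs and illustrates direction, not expected size. The documents do not show that escalation will occur, nor that it would go wholly unnoticed. This is an inexpensive improvement to a pilot that already limits its clinical outcomes to description.

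**What to change.** In the SAP:

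1. Define the RCT ADU outcome: measure, cut-off, and how several substances are combined. Reconcile the entry rules in Sections C.3 and C.6, and say whether the baseline value is the survey result or the RCT baseline assessment.
2. Report by arm, descriptively, with intervals that allow for clinic clustering:
   - number and percentage whose NM-ASSIST risk level rises, and number and percentage whose level falls, from baseline to 6 months;
   - change in NM-ASSIST score;
   - urine conversions in both directions, noting the short alcohol detection window in Section C.5 (8 to 80 hours).
3. State that change in ADU is read in both directions and against the control arm.
4. Withdrawal frequency from bank statements may be described in the intervention arm, labelled exploratory. Diaries are voluntary and should not be used to infer harm, since who keeps one may depend on use.

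The cost is a few tables from data already planned. No tests, visits or instruments are added, and no change to the spending rule is proposed.

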
#### C.7.1 Quantitative Data analysis.

**Analysis of cross-sectional survey data:** Frequency distributions and summary statistics for the outcome and all predictor variables will be derived. The prevalence of ADU from both biological tests and self-reports, assessed using the Smoking and Substance Involvement Screening Test (NIDA-Modified ASSIST) among AYLHIV, will be calculated by dividing the number who tested positive for ADU by the total number of participants tested, and dividing the number screened to be of moderate or high risk in self-reported data by the total number of participants who completed the survey. To determine which multilevel factors are associated with substance misuse, we will fit logistic regression models comprising the outcome (ADU) and potential risk factors with standard errors adjusted for clustering by clinics.

**Analysis of RCT data:** Primary hypothesis. We hypothesize that participants in the intervention group will have a lower odds of ADU compared to participants in the control group. To test this hypothesis, we will fit three-level mixed-effects models. Each model will comprise the outcome, and fixed categorical effects for study group (intervention vs control), time (baseline, 6-months), and a group-by-time interaction term. Random intercepts will be fitted at the clinic and person level, with unstructured correlations among subjects' repeated measures. Robust Huber-White standard errors and test statistics will be computed for each model. We will assess the omnibus effects for study group, time, and their interaction. Post-estimation analyses will be conducted to assess time-within group simple effects and group within time simple effects. Secondary hypothesis. We hypothesize that AYLHIV in the intervention group will have better mental health outcomes including lower levels of

depressive symptoms, less hopelessness, improved adherence and achieve better viral suppression and improved economic outcomes than AYLHIV in the control group.

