### Study objectives

The proposed study will investigate the following specific aims:

**Aim 1a.** Examine the prevalence and consequences of ADU in a cohort of 200 AYLHIV (ages 18-24) seen at six (6) HIV clinics in southwestern Uganda. We will utilize adolescent self-reports and biological measures of alcohol and drug use (urine).

**Aim 1b.** Using a mixed methods approach, identify the multi-level (individual, interpersonal, community and structural) factors associated with ADU among AYLHIV

**Aim 2:** Using a subset of the sample, explore the feasibility and short-term effects of a economic empowerment intervention on ADU among AYLHIV.

Our long-term goal is to better understand the epidemiology and consequences of ADU among AYLHIV in high-risk environments and evaluate a culturally tailored intervention that could prevent harmful ADU and improve the overall and long-term health and well-being of AYLHIV. The proposed study will be conducted in fishing communities located in three districts of the greater Masaka region of southwestern Uganda - a region heavily affected by HIV (12% prevalence vs national average of 6.2%) and high rates of household poverty and

alcohol/drug use. The findings from this proposed study will contribute to our understanding of the epidemiology, risk and resilience factors and consequences of alcohol and drug use among AYLHIV, in order to inform the development of effective ADU prevention intervention. If warranted, these findings will inform the design of an R01 grant to examine the long-term effects of a family-based economic empowerment intervention on ADU among AYLHIV.

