## RESEARCH STRATEGY

### A.1. SIGNIFICANCE.

**Adolescent alcohol and drug use (ADU) is a significant public health challenge in SSA.** About 41.6% of adolescents in SSA have used at least one psychoactive agent. Alcohol is the most commonly used drug; one third of adolescents have used alcohol in their lifetime, 22.5 million are current drinkers, and over 50% engage in heavy episodic drinking. Alcohol use nearly doubles during the transition to adulthood, from 21.4% of adolescents aged 16-19 to 34.1% of young adults aged 20-24 years. Uganda, one of the poorest countries in SSA, has the second highest rate of per capita alcohol consumption in SSA (15.1 liters of pure alcohol vs regional average of 6.2 liters of pure alcohol). Over 30% of Ugandan adolescents and youth have used alcohol and about 20% misuse alcohol. These estimates reach even greater magnitudes in the country's fishing villages – a key HIV vulnerable population- where ADU is normative. A few studies have assessed ADU among AYLHIV. A study conducted in Rwanda found that 61% of AYLHIV receiving medication from a clinic had drunk alcohol within 6 hours prior to having sex. In South Africa, a prior study found that 53.8% of the male AYLHIV and 5% of female AYLHIV had ever used drugs. In Uganda, a recent cross-sectional study of 479 adolescents aged 12 – 17 years found that 5.9% reported use of at least one psychoactive substance, including alcohol (4.3%), marijuana (2.1%) and other drugs (2.1%) such as cocaine, glue and heroine. ADU is a key driver of new HIV infections and poor HIV care outcomes in SSA. It is associated with HIV risk behaviors such as increased sexual risk-taking, unprotected sex, early sexual debut, an increased number of sexual partners, resulting in transmission of HIV. ADU is also associated with sub-optimal mental health e.g. depression and suicidal ideation. Among AYLHIV, ADU impedes adherence to anti-retroviral therapy (ART), retention in care, and viral suppression. Among HIV-infected adults, ADU have been shown to increase susceptibility to AIDS mortality, even among HIV virally suppressed and medication adherent persons.

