#### C.4. Recruitment of participants and informed consent.

Recruitment strategies will build on RTY (local implementing partner) and ICHAD's long-standing relationships (>15 years) with 39 health clinics in the greater Masaka region. We will capitalize on recruitment procedures tested in previous SUUBI studies that involve collaborating with health clinics in the region (namely Suubi+Adherence: 1R01HD074949-01, Suubi+Adherence-R2: R01HD074949-07, and Suubi4Stigma: R21MH121141). All participants will be recruited from the selected HIV clinics. For the cross-sectional survey, 200 AYLHIV will be recruited from across six clinics located in the greater Masaka region. The designated study contact at each health clinic will present the project to all eligible AYLHIV 18-24 years during their clinic visits. If there is interest, they will provide verbal consent to be contacted by the research study team. The study coordinator will contact interested AYLHIV to inform them about, the required extent of participation, the risks and benefits of participating, and to ask any questions. Written informed consent will be obtained from AYLHIV 18-24 years and from healthcare providers >18 years to participate. The written consent documents will emphasize the following elements: 1) participation in the study is voluntary; 2) responses to study questions are confidential; 3) participants can terminate their participation at any time and their decision to withdraw from the study will not affect their access to services they are currently receiving in any way; 4) participants may be contacted to participate in the RCT if eligible. A screening tool will be developed to assess whether participants meet the study inclusion criteria. Participants' data will be protected by a Certificate of Confidentiality, which protects the privacy of research subjects by prohibiting disclosure of identifiable, sensitive research information to individuals not involved in the research unless the participant consents.

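### The Aim 1b survey regression clusters on six clinics and names no small-sample method; with a normal reference, null factors would be flagged about 10–16% of the time at a nominal 5%

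*Protocol*

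**What the plan says.** Aim 1b is to "identify the multi-level (individual, interpersonal, community and structural) factors associated with ADU among AYLHIV". The data come from the cross-sectional survey: under Study objectives, Aim 1a describes a "cohort of 200 AYLHIV (ages 18-24) seen at six (6) HIV clinics in southwestern Uganda", and Protocol C.4 repeats that "200 AYLHIV will be recruited from across six clinics located in the greater Masaka region". No numbers per clinic are given.

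The analysis is set out in one sentence of Protocol C.7.1. Its purpose is "To determine which multilevel factors are associated with substance misuse" and its method is "we will fit logistic regression models comprising the outcome (ADU) and potential risk factors with standard errors adjusted for clustering by clinics". The sentence does not give the variance estimator, any finite-cluster correction, the reference distribution or the significance level. The SAP covers feasibility, acceptability and descriptive summaries of the pilot RCT. Its statement that pilot trials are too small for formal tests concerns the RCT, so it neither specifies nor withdraws the survey regression.

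**The concern.** A cluster-robust variance is justified as the number of clusters grows, and here there are six. The middle of the sandwich is built from six clinic score totals. Those totals sum to zero at the fitted estimate, so at most five are free. Two errors follow if the ordinary form is used with a normal reference: the standard error tends to be too small, and 1.96 ignores how poorly that standard error is estimated. Both push towards false positives and short intervals.

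At stake is the list of factors the study reports as associated with alcohol and drug use. As an illustration, Table 1 of the Protocol lists about 26 individual and interpersonal factors by my count. If all were null and each were tested once, the expected number of false positives would be 26 × 0.05 = 1.3 at the nominal rate, and 26 × 0.10 = 2.6 to 26 × 0.16 = 4.2 at the inflated one. The Protocol says the findings are to inform prevention work and, if warranted, a larger grant.

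**Working it through.** The plan states no error rate for this analysis, so there is no figure to reproduce.

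**Inputs from the documents.** G = 6 clinics and n = 200 (Study objectives; C.4). Two Protocol figures bracket prevalence: the statement in A.1 that "about 20% misuse alcohol", and the 100 ADU-positive participants that C.6 expects from the 200 surveyed (100/200 = 50%).

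**Assumptions.** Sandwich variance; two-sided 5%; prevalence 0.20, 0.35 or 0.50; outcome ICC (logit scale) and predictor ICC of (0, 0), (0.05, 0.05) or (0.10, 0.20); 1, 5 or 10 normal predictors. Clinic sizes are equal (33–34), moderately unequal (60/45/35/25/20/15) or strongly unequal (100/40/25/15/12/8).

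**Step 1, approximation by hand.** Treat the statistic as t on G − 1 = 5 degrees of freedom but compare it with 1.96.
- With the G/(G−1) factor: P(|t₅| > 1.960) = 10.7%.
- Without it, the standard error shrinks by √(5/6), so the effective cut-off is 1.960 × √(5/6) = 1.789 and P(|t₅| > 1.789) = 13.4%.

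**Step 2, simulation.** 81 scenarios, 3,000 runs each, Monte Carlo standard error about 0.6 points. Rejection of a null individual-level factor:

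| Method | Equal | Moderate | Strong |
|---|---|---|---|
| No factor, normal | 12.9–16.9% | 13.9–19.3% | 17.4–22.0% |
| G/(G−1), normal | 10.2–13.6% | 10.7–16.4% | 14.7–18.3% |
| G/(G−1), t(5) | 4.6–7.0% | 4.9–8.8% | 7.7–10.0% |
| Jackknife, t(5) | 3.1–5.0% | 3.7–5.2% | 3.6–6.3% |

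Coverage is 100% minus rejection. Across equal and moderate clinics it is 83.6–89.8% with the factor and 80.7–87.1% without.

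**Step 3, dependence on the assumptions.** Smaller sets of scenarios, run separately with equal and moderate clinics, gave lower ends of about 10% and upper ends of 13.4–15.3% with the factor and a normal reference. With both ICCs at zero, one predictor and equal clinics, rejection was still 9.8% with the factor and 12.4% without. The inflation therefore comes mainly from having six clusters, not from the assumed ICCs.

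**Step 4, factors that vary only between clinics.** A null clinic-level factor was rejected in 23–30% of runs with a normal reference and in 15–17% even with t(5).

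**Step 5, clinic fixed effects as an alternative.** With model-based standard errors and a common slope, rejection was 4.4–6.5% (among converged fits, 64–100% of runs). When the factor's effect varied between clinics around zero, rejection rose to 12.0–14.2% (slope SD 0.3) and 21.0–24.0% (slope SD 0.5). Jackknife with t(5) stayed at 3.7–5.5%.

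**The case against.** The strongest reply is that the error is conditional. C.7.1 does not say that a normal reference will be used. With t(5) and the ordinary clustered error, individual-level factors come to 4.6–8.8% in equal or moderately unequal clinics, so what the documents show is an unspecified method and the error rate rests on assumptions. That is fair, and the rates should be read that way. It does not clear the plan, because the sentence as written permits analyses whose error rates differ two- to threefold. Even t(5) leaves 7.7–10.0% when clinic sizes are very uneven.

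A second reply is that the analysis is exploratory, feeds into a mixed-methods interpretation and has no bearing on RCT entry. That limits the consequence, and it stands. Aim 1b is nevertheless a named aim, and intervals that cover 84–90% when labelled 95% misstate uncertainty in exploratory work too.

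Third, the jackknife is mildly conservative in some scenarios (3.1%) and costs power, so preferring it to t(5) alone is partly a judgement. That also stands.

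Two limits remain. No multiplicity rule is stated for the many factors, and this change does not supply one. The scenarios also ignore the selection of two clinics per district.

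**Conclusion.** The concern holds. It is certain that a six-cluster analysis is planned with no small-sample method named. If that analysis is a sandwich variance with a normal reference at two-sided 5%, a null individual-level factor is flagged about 10–16% of the time with the G/(G−1) factor and equal or moderately unequal clinics. That is roughly two to three times the nominal rate, and it is higher without the factor or with very uneven clinics. These are simulated ranges under assumed clinic sizes, ICCs and predictors, not ceilings. Confidence in the exact size is medium. The point should be fixed, but its reach is limited to Aim 1b; the RCT comparison and the feasibility outcomes are untouched.

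**What to change.** In the survey paragraph of C.7.1:

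- Name a bias-corrected cluster variance, for example the leave-one-clinic-out jackknife. Take tests and intervals from a t distribution on at most 5 degrees of freedom, and state the alpha.
- Use clinic fixed effects with model-based standard errors as a sensitivity analysis only. State that they assume the factor's effect is the same in every clinic, and that a clinic with no cases, or only cases, drops out.
- Report any factor that varies only between clinics descriptively, without a test.

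**Cost.** One or two sentences and no new data. Section D of the Protocol scheduled the survey analysis for December 2022 to January 2023, so if it has been done it must be re-run and the change of method disclosed.

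Jackknife t(5) intervals are 33–63% wider than the normal-reference clustered interval (equal or moderate clinics). With 5 predictors, prevalence 0.35 and ICCs of 0.05, detection of an assumed odds ratio of 1.5 per SD falls from 73–74% to 44–46%, and of 2.0 from 98% to 84–86%. The higher figures belong to a test with an inflated error rate. Using t(5) with the ordinary clustered error is cheaper, at 2.571/1.960 = 1.31 times the width, and removes most but not all of the inflation.
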